8.9.1 Immunogenicity assessments

Blood samples for the measurement of ADA_b and neutralizing antibodies will be collected. A total of 9mL will be collected at timepoints for which PK, ADA_b, and neutralizing antibodies are all measured. Immunogenicity data will not be sent to the Investigator to protect the blinded nature of the treatment assignments and response.

Antibodies to bimekizumab will be evaluated in plasma samples collected from all participants according to the Schedule of Activities. Additionally, plasma samples should also be collected at the final visit from participants who discontinued IMP or were withdrawn from the study. These samples will be tested by the Sponsor or Sponsor's designee.

Plasma samples will be screened for antibodies binding to bimekizumab and the titer of confirmed positive samples will be reported. Other analyses may be performed to verify the stability of antibodies to bimekizumab and/or further characterize the immunogenicity of bimekizumab.

The detection and characterization of antibodies to bimekizumab will be performed using validated assay methods by or under the supervision of the Sponsor. All samples collected for detection of antibodies to bimekizumab will also be evaluated for bimekizumab plasma concentration to enable interpretation of the antibody data. Antibodies may be further characterized and/or evaluated for their ability to neutralize the activity of bimekizumab. Samples may be stored for a maximum of 20 years (or according to local regulations) following the last study participant's last visit for the study at a facility selected by the Sponsor to enable further analysis of immune responses to bimekizumab.

8.10 Medical resource utilization and health economics

Health-related outcomes and medical resource utilization will be collected as part of standard eCRF pages during the study (eg, concurrent medical procedures, concomitant medications, hospitalizations, WPAI-SHP).

8.11 Photography

At certain sites, where feasible, representative photographs of the changes in skin will be captured. Photographs will be anonymized. This is optional for study participants and requires a separate informed consent. A decision not to consent does not exclude the study participant from the study.

9 STATISTICAL CONSIDERATIONS

A description of statistical methods follows and will be described in more detail in the Statistical Analysis Plan (SAP).

9.1 Definition of analysis sets

9.1.1 Enrolled Set

The Enrolled Set will consist of all study participants who have given informed consent.

9.1.2 Randomized Set

The Randomized Set (RS) will consist of all randomized study participants.

9.1.3 Safety Set

The Safety Set will consist of all study participants who received at least 1 full or partial dose of IMP and will be used for the demographic, safety, and immunogenicity analyses.

9.1.4 Full Analysis Set

The Full Analysis Set (FAS) will consist of all study participants who received at least 1 dose (full or partial) of IMP and had a valid Baseline measurement and a post-Baseline measurement for abscess, inflammatory nodules, and draining tunnel counts.

9.1.5 Per-Protocol Set

The Per-Protocol Set will consist of all study participants in the FAS who had no important protocol deviations affecting the primary efficacy variable. Important protocol deviations will be predefined and study participants with important protocol deviations will be evaluated during ongoing data cleaning meetings prior to unblinding of the data.

9.1.6 Pharmacokinetics Per-Protocol Set

The Pharmacokinetics Per-Protocol Set will consist of study participants who received at least 1 full dose of bimekizumab and provided at least 1 quantifiable plasma concentration post-dose without important protocol deviations that would affect the PK. The Pharmacokinetics Per-Protocol Set is defined separately for each of the treatment periods (ie, separately for the Initial Treatment Period and the Maintenance Treatment Period).

9.1.7 COVID-19 Free Set

The COVID-19 Free Set will consist of all study participants randomized into the study and who have no COVID-19 impact through Week 16. This analysis set will be used for sensitivity analysis of the primary efficacy endpoint.

9.2 General statistical considerations

All analyses will be performed using SAS® version 9.4 or later (SAS Institute, Cary, NC, US).

Descriptive statistics will be used to provide an overview of the Baseline, efficacy, and safety results. For categorical parameters, the number and percentage of study participants in each category will be presented by treatment group. The denominator for the percentages will be based on the number of study participants appropriate for the purpose of analysis. Unless otherwise noted, all percentages will be expressed to 1 decimal place. For continuous parameters, descriptive statistics will include n, mean, standard deviation, median, minimum, and maximum. Two-sided 95% confidence intervals, geometric means, and coefficient of variation will be presented for selected variables as appropriate.

Baseline for each assessment is defined as either the value obtained at Baseline or the last available value obtained prior to treatment administration (details to be specified in the SAP).

Formal statistical testing will be conducted for this study for the primary and secondary efficacy variables. Other efficacy variables will be summarized descriptively by treatment arm. P-values and confidence intervals may be produced for other or exploratory variables but will be interpreted as non-inferential (ie, nominal). Additionally, other analyses will be conducted as deemed appropriate and described in the SAP.

The primary treatment comparison for all formal statistical analyses of efficacy will be between bimekizumab and placebo.

9.3 Planned efficacy/outcome analyses

9.3.1 Analysis of the primary efficacy endpoint

The primary objective of this randomized, double-blind, placebo-controlled, multicenter, pivotal study in study participants with moderate to severe HS is to compare the efficacy of bimekizumab [REDACTED] and bimekizumab [REDACTED] with placebo at Week 16. For the purposes of Week 16 analyses, the bimekizumab treatment arms of [REDACTED] and bimekizumab [REDACTED] treatment groups will be pooled.

The primary and secondary efficacy analyses will be performed based on the RS.

The primary endpoint is the HiSCR₅₀ response at Week 16. The primary efficacy analysis will evaluate the composite estimand in the RS. The composite estimand combines the clinically meaningful improvement from Baseline based on the HiSCR₅₀ response and early receipt of

systemic antibiotic rescue medication, or discontinuation of IMP due to an AE or lack of efficacy.

The following 4 attributes describe the estimand that will be used to define the treatment effect of interest for the primary efficacy analysis:

1. Population=Study participants meeting the protocol-specified inclusion/exclusion criteria.
2. Study participant-level outcome=HiSCR₅₀ at Week 16.
3. Intercurrent event handling=An intercurrent event is defined as receipt of systemic antibiotic rescue medication or discontinuation of study treatment due to an AE or lack of efficacy prior to Week 16. A composite strategy will be implemented in which a positive clinical outcome is defined as achieving HiSCR₅₀ at Week 16 and not receiving systemic antibiotic rescue medication, and not discontinuing study treatment due to an AE or lack of efficacy through Week 16. Any missing data at Week 16 that are not preceded by an intercurrent event will be imputed using multiple imputation.
4. Population-level summary measure=conditional odds ratio comparing bimekizumab to placebo adjusted for stratification factors used in the randomization.

As a sensitivity analysis, any missing data at Week 16 that are not preceded by an intercurrent event (ie, receipt of systemic antibiotic rescue medication, or discontinuation of IMP due to an AE or lack of efficacy) will be imputed as non-response.

The statistical hypothesis for the HiSCR₅₀ response at Week 16 is that the conditional odds ratio for the HiSCR₅₀ response in the bimekizumab treatment group relative to the placebo group is equal to 1.

A logistic regression model will be used to assess the effect of bimekizumab vs placebo on HiSCR₅₀ response. The model will include a fixed effect for treatment. The stratification variables of Hurley stage and prior antibiotic use will be added to the model unless inappropriate. The odds ratio versus placebo, p-value (from Wald test), and confidence interval will be calculated.

To assess the impact of the COVID-19 pandemic on the primary efficacy endpoint analysis, additional sensitivity analyses will be performed as specified in Section 9.3.4.

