6.5.2 Prohibited concomitant treatments (medications and therapies)

The following concomitant medications and therapies are prohibited during the study (also see Table 6–3):

- All biologic therapy with a potential therapeutic impact on the disease being studied, including those listed in Table 6–3.
- Phototherapy (psoralen and ultraviolet A and/or ultraviolet B) or photochemotherapy.
- Immunomodulatory therapy, including topical or systemic steroids except as noted in Section 6.5.3.1 (Rescue Medications/Lesion Intervention), and Table 6–3.
- Topical and systemic therapies for HS (see Table 6–3).
- Surgical or laser intervention for an HS lesion except as outlined in Section 6.5.3.1 (Rescue Medications/Lesion Intervention).

Table 6–3: Exclusions for prior medications

Drug class	Exclusion criteria
Systemic antibiotics	Used within 2 weeks prior to the Baseline Visit. Note: See exception for permitted, stable doses of antibiotics in Section 6.5.1.
Systemic retinoids	Used within 4 weeks prior to the Baseline Visit
Systemic treatment (non-biologic) 
 • Apremilast • Systemic immunosuppressant agents (eg: methotrexate, cyclosporine, azathioprine, thioguanine) • Systemic fumarate • Systemic oral or injectable corticosteroids • Phototherapy and radiotherapy (eg, psoralen and ultraviolet A and/or ultraviolet B) or photoradio/chemotherapy 	Used within 4 weeks prior to the Baseline Visit. Note: See exception for permitted, stable doses of antibiotics in Section 6.5.1.
Anti-tumor necrosis factors (including biosimilars) adalimumab, etanercept, certolizumab, golimumab, infliximab	Used within 12 weeks prior to the Baseline Visit. Note: For etanercept, used within 1 month prior to the Baseline Visit.
Other biologics Abatacept Anakinra Natalizumab Belimumab Tocilizumab Efalizumab Or other biologics approved by regulatory agencies after the protocol is approved	Used within 12 weeks prior to the Baseline Visit Note: for other biologics approved by regulatory agencies after the protocol is approved: Washout of 6 months prior to the Baseline Visit or 5 half-lives prior to the Baseline Visit, whichever is greater.
Secukinumab, brodalumab, ixekizumab and other IL-17 inhibitors approved by regulatory agencies after the protocol is approved	Washout of 6 months prior to the Baseline Visit or 5 half-lives prior to the Baseline Visit, whichever is greater.

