6.5.3.2 Rescue Medications/Lesion Intervention

There are no absolute restrictions on the use of rescue medications for study participants whose HS deteriorates during the study. While the objectives of the study should be protected as much as possible through observance of the restrictions detailed above in Section 6.5, the well-being of the study participant will always take priority; study participants should be managed as deemed appropriate by the Investigator.

In the event an acutely painful lesion occurs that requires an immediate intervention, Investigators will have the option to perform interventions. Interventions can include analgesics for a limited period of time (see below), intralesional injections of triamcinolone, and/or incision and drainage of the abscess. Intralesional injections of triamcinolone (up to 20mg across all lesions at a given visit, and using a concentration of no more than 20mg/mL [suspension for injection]) must be consistent with the maximum number of interventions described below and clinical practice. Concomitant use of wound care dressings is permitted; however, options are limited to alginates, hydrocolloids, and hydrogels. Concomitant medications associated with the lesion intervention(s) must be captured in source documents and on the appropriate eCRF.

Any analgesic that is initiated (new analgesic, new class of analgesic, increased dose of an analgesic stable since Baseline, regardless of duration of treatment) after Baseline (first day of study drug administration) will be considered rescue pain medication for the Initial Treatment Period and Maintenance Treatment Period (Weeks 0 to 48).

A total of 2 protocol-allowed interventions are permissible during the Initial Treatment Period (from Baseline Visit to Week 16). Do not include analgesic rescue treatment in the number of protocol-allowed interventions. An intervention can occur on maximally 2 different lesions at the same visit, or on the same lesion at 2 different study visits. The same lesion cannot be treated

2 times at the same visit. If a study participant requires more than 2 interventions within the first 16 weeks of the study, then the study participant should be discontinued from the study.

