7.2 Participant discontinuation/withdrawal from the study

Note: For female study participants, please see Section 8.3.5 for pregnancy that occurs during the study as evidenced by a positive pregnancy test.

Study participants are free to withdraw from the study at any time, without prejudice to their continued care.

A study participant may withdraw from the study at any time at his or her own request, or may be withdrawn at any time at the discretion of the Investigator for safety, behavioral, compliance, or administrative reasons.

If the study participant withdraws consent for disclosure of future information, the Sponsor may retain and continue to use any data collected before such a withdrawal of consent.

If a study participant withdraws from the study, he or she may request destruction of any samples taken and not tested, and the Investigator must document this in the site study records.

See the Schedule of Activities (Table 1–1) for data to be collected at the time of study discontinuation and follow-up and for any further evaluations that need to be completed.

If a study participant does not achieve a partial response (defined as a $\geq 25\%$ reduction in AN count from Baseline [Week 0]) at any visit from Week 32 to 46, the Investigator should contact the Medical Monitor to discuss whether the study participant should continue on study.

Study participants will be withdrawn from the study, after being encouraged to complete the Premature End of Treatment (PEOT) and the SFU Visit if either of the following events occur:

1. Study participant withdraws his or her consent.
2. The Sponsor or a regulatory agency requests withdrawal of the study participant.

Study participants should be withdrawn from IMP and encouraged by the Investigator to return for all scheduled visits through Week 48, and the SFU Visit (if the Week 48 Visit is ≥ 20 weeks after the final dose of IMP, the SFU Visit is not required) if any of the following events occur:

1. Study participant develops an illness that would interfere with his or her continued participation.
2. Study participant is noncompliant with the study procedures or medications in the opinion of the Investigator.
3. Study participant takes prohibited concomitant medications as defined in this protocol (Section 6.5.2) that may present a risk to the safety of the participant or the integrity of the study data, in the opinion of the Investigator and/or the Medical Monitor and/or UCB study physician.

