3. The treatment policy strategy for addressing intercurrent events will be considered. This will be based on an analysis of all available data at Week 16 regardless of the occurrence of intercurrent events. This analysis will use the same models specified for the primary analysis, where study participants are analyzed according to their randomized treatment, even if they discontinued study treatment for any reason prior to Week 16. Even though efforts will be made to collect the primary outcome data for all study participants at Week 16, there may still be some study participants for whom Week 16 efficacy data cannot be obtained. In this case, missing data will be imputed using multiple imputation under the assumption of MAR. Results will be combined into a single inference using Rubin's rule. It should be noted that this measures something different from the primary analysis and could be confounded by placebo study participants who withdraw and are subsequently on another active medication at the time of the Week 16 assessment. Therefore, the results of this analysis should be interpreted in the appropriate context.

4. An additional supportive analysis will be based on observed data only for study participants who are still on the randomized treatment at Week 16. Study participants with missing data or who have prematurely discontinued study treatment will be treated as missing. The same procedure described as in the primary efficacy analyses will be used.

All imputation of other missing data will be detailed in the SAP.

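### The primary composite fails a participant for a new systemic antibiotic but not for a prohibited systemic steroid, immunosuppressant or biologic taken before Week 16

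*Protocol*

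**What the plan says.** Section 9.3.1 defines the events in closed form, for the time before Week 16: "An intercurrent event is defined as receipt of systemic antibiotic rescue medication or discontinuation of study treatment due to an AE or lack of efficacy". The success rule repeats the same events, asking for a Week 16 HiSCR50 together with "not receiving systemic antibiotic rescue medication, and not discontinuing study treatment due to an AE or lack of efficacy through Week 16". For everyone else only missing values are touched: "Any missing data at Week 16 that are not preceded by an intercurrent event will be imputed using multiple imputation". Observed Week 16 values are used as they stand.

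Section 6.5.2 prohibits, among other things, "All biologic therapy with a potential therapeutic impact on the disease being studied, including those listed in Table 6–3" and "Immunomodulatory therapy, including topical or systemic steroids except as noted in Section 6.5.3.1". It also bars topical and systemic HS therapies by reference to Table 6-3. That table lists systemic immunosuppressants, systemic corticosteroids, biologics and Janus kinase inhibitors, and also topicals, disinfectants and herbal products.

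Section 6.5.3.2 opens with "There are no absolute restrictions on the use of rescue medications for study participants whose HS deteriorates during the study". It then asks that the Section 6.5 restrictions be observed as far as possible, with the participant's well-being taking priority.

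Section 7.2 item 3 asks for withdrawal from study drug when "Study participant takes prohibited concomitant medications as defined in this protocol (Section 6.5.2) that may present a risk to the safety" or to data integrity, in the opinion of the Investigator, Medical Monitor or study physician. Such participants are encouraged to attend all visits through Week 48.

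Section 9.6 warns that the supportive treatment-policy analysis "could be confounded by placebo study participants who withdraw and are subsequently on another active medication at the time of the Week 16 assessment", and says that analysis measures something different from the primary one.

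**The concern.** The composite is meant to stop a participant being credited with a response that another treatment may have produced. It does so for systemic antibiotics. For the more potent systemic classes in Section 6.5.2 it does so only if the participant also receives a systemic antibiotic, or stops study drug with AE or lack of efficacy as the recorded reason. Otherwise, an observed HiSCR50 on one of those drugs is a response in the randomised arm.

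HiSCR75 and pain response inherit the gap, since Section 9.3.2 analyses them like the primary endpoint. Flare is analysed in the same manner, but there the event is the bad outcome.

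At stake are the interpretation of the estimand and some effect size. Need for other therapy would plausibly be greater on placebo, which has only 70 participants and serves both dose comparisons.

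**Working it through.** **Following the text.** Take a participant given a prohibited systemic HS-active drug before Week 16.

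| Path | Listed event in 9.3.1? | Week 16 HiSCR50 met, scored as |
|---|---|---|
| Also starts a systemic antibiotic | Yes | Non-response |
| Study drug stopped, reason recorded as AE or lack of efficacy | Yes | Non-response |
| Study drug stopped under 7.2 item 3, reason recorded as prohibited medication; attends Week 16 | No | Response |
| Not judged a risk under item 3, stays on study drug | No | Response |
| No Week 16 data, no listed event | No | Multiple imputation |

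The third and fourth rows are the gap.

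**Reproducing the plan's power.** Inputs from Section 9.8 and Table 9-1 are HiSCR50 rates of 0.25 (placebo, N=70), 0.50 (N=140) and 0.60 (pooled, N=280), at two-sided alpha 0.025 (z = 2.2414). The formula is

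power = Φ{[(p1 − p0) − z·SE0] / SE1}, with SE0 from the pooled proportion and SE1 from the separate proportions.

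- 140 vs 70: pooled proportion 0.4167, SE0 = 0.0722, SE1 = 0.0668. (0.25 − 2.2414 × 0.0722)/0.0668 = 1.32, so power is 0.907. The protocol states 0.90.
- 280 vs 70: SE0 = 0.0667, SE1 = 0.0595, power 0.9996. The protocol states 0.99.

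Both figures reproduce and neither is disputed.

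**Illustrating the gap.** The documents give no usage rate, so everything below is assumed. Let x_p and x_b be the shares of placebo and bimekizumab participants who take such therapy without a listed event. Let r be the share of them who then meet HiSCR50 although they would otherwise be non-responders. Take the planned rates as those that apply when users count as failures. Then p0 = 0.25 + x_p·r, and p1 = 0.50 + x_b·r or 0.60 + x_b·r. The range in each row runs over r = 0.3 to 0.5.

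| x_p / x_b | Placebo rate | Power, 140 vs 70 | Power, 280 vs 70 |
|---|---|---|---|
| 0 / 0 | 0.25 | 0.907 | 0.9996 |
| 2% / 1% | 0.256-0.260 | 0.897-0.891 | above 0.999 |
| 5% / 1% | 0.265-0.275 | 0.869-0.840 | 0.999-0.998 |
| 5% / 2% | 0.265-0.275 | 0.878-0.856 | 0.999 |
| 5% / 5% | 0.265-0.275 | 0.902-0.900 | above 0.999 |
| 10% / 2% | 0.280-0.300 | 0.824-0.752 | 0.998-0.995 |
| 10% / 4% | 0.280-0.300 | 0.845-0.795 | 0.999-0.997 |

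At 10% / 2% and r = 0.5 the odds ratio falls from 3.00 to 2.43 (140 vs 70) and from 4.50 to 3.65 (280 vs 70). In people, the placebo shift is 70 × 0.05 × 0.3 ≈ 1 to 70 × 0.10 × 0.5 = 3.5 at 5-10% use, and under 1 at 2% use.

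**The case against.** The strongest reply is that this is a deviation, not a planned route. A reader might infer from the opening of Section 6.5.3.2 that sites may give systemic steroids or biologics as rescue. The documents do not support that: the next sentence asks for the Section 6.5 restrictions to be observed, and the rescue options named are systemic antibiotics, analgesics, intralesional triamcinolone, and incision and drainage. This stands. The wording is loose, but it does not authorise prohibited systemic drugs.

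Many users would also be caught already. A drug given for deteriorating HS may well lead to study drug being stopped and recorded as lack of efficacy, or come with a systemic antibiotic. This stands too, and it shrinks the group. It does not empty it, because item 3 of Section 7.2 is a separate reason and rests on judgement.

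The Per-Protocol Set (Section 9.1.5) may exclude some users as important deviations, and supportive analysis 4 in Section 9.6 treats those off study drug as missing. Both examine the case in part, but neither is the primary analysis.

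A reader might also take Section 9.6 to say that the primary analysis is free of this confounding. It does not say so, and for stops due to AE or lack of efficacy its contrast with the treatment-policy analysis is right. It is only silent on the users described here.

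The point cannot be left to the SAP as missing detail. The protocol states the list as a definition, so adding an event later would change the primary estimand.

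**Conclusion.** The gap is real and follows from the text as written. Its size cannot be determined from the documents and is probably small. On the assumed rates, power for the N=140 comparison drops by one to two points at 2% / 1% use, hardly at all if use is equal at 5%, and to 0.75-0.88 at 5-10% placebo and 1-4% active use. The pooled comparison is not at risk for power, though its odds ratio would be diluted.

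A reader might infer that the primary result could be falsely positive. The documents give no ground for that: if use is commoner on placebo, the bias is towards no difference. The case for acting is that the estimand treats a systemic antibiotic more severely than a systemic steroid or biologic, and that correcting this costs little.

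**What to change.** In Section 9.3.1, add one intercurrent event under the same composite strategy: receipt before Week 16 of prohibited systemic HS-active therapy (systemic corticosteroid, systemic immunosuppressant or other non-biologic systemic HS therapy, biologic, Janus kinase inhibitor), or discontinuation of study drug because of it.

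- State that permitted lesion interventions (intralesional triamcinolone, incision and drainage), analgesics, topicals, disinfectants and herbal products are not part of this event. Pointing to the whole of Table 6-3 would fail participants for a procedure that Section 6.5.3.2 allows.
- Apply it as non-response for HiSCR50, HiSCR75 and pain response, and as the unfavourable outcome (flare) for the flare endpoint. For DLQI and pain change, handle it in the same way as the other intercurrent events.
- Identify cases by blinded review of recorded concomitant medications and discontinuation reasons before unblinding.
- Amend the caveat in Section 9.6 to match.

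The sponsor must also reconcile Sections 6.5.2, 6.5.3.2 and 7.2 item 3, including the reference in 6.5.2 to 6.5.3.1 under the title that belongs to 6.5.3.2. No clinical rule is proposed here.

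The cost is wording and one blinded medication review, with no new procedures or participants. A few participants would move from responder to non-responder.
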